#### 6.14.1. Extent of Exposure

Duration of exposure to study treatment will be summarized by treatment group for the Modified Safety Population and the Safety Population.

The duration of exposure will be calculated as:

$$\begin{aligned} & \textit{Duration of exposure (days)} \\ &= \textit{Date of last visit (scheduled or unscheduled) in the specified Treatment Period} \\ & \quad - \textit{Date of first dose in Treatment Period} + 1 \end{aligned}$$

Drug interruption time period due to the use of systemic rescue therapies will be removed from study drug exposure calculations as described in compound level safety plan.

The number and percentage of patients in each of the following categories will be included in the summaries:

- >0, ≥7 days, ≥14 days, ≥30 days, ≥60 days, ≥90 days, ≥112 days, ≥120 days. Note that patients may be included in more than 1 category.
- >0 to <7 days, ≥7 to <14 days, ≥14 to <30 days, ≥30 to <60 days, ≥60 to <90 days, ≥90 to <112 days, ≥112 to <120 days, ≥120 days.

Additional exposure ranges may be considered if necessary. No p-values will be reported.

The summaries will also include the following information:

- Total exposure in patient years, calculated as:

$$\begin{aligned} & \text{Total exposure in patient years} \\ &= \frac{\text{Sum of exposures for all patients in treatment group}}{365.25} \end{aligned}$$

- Mean and median total dose. Total dose (in mg) is calculated by the number of active injections taken during the treatment period multiplied by dose. The total dose (in mg) taken during Treatment Period will be calculated as follows: *Total lebrikizumab dose = Total number of active injections (including loading doses, if any) received in Treatment Period × 250*
- The total number of injections administered will be based on the prompt “Please select the number of syringes successfully injected” in the Dosing Diary eCRF page.

### 6.14.2. Adverse Events

A TEAE is defined as an event that first occurred or worsened in severity after baseline. The MedDRA Lowest Level Term (LLT) will be used in the treatment-emergent computation. The maximum severity for each LLT during the baseline period will be used as baseline. The treatment period will be included as postbaseline for the analysis. For events with a missing severity during the baseline period, it will be treated as ‘mild’ in severity for determining treatment-emergence. Events with a missing severity during the postbaseline period will be treated as ‘severe’ and treatment-emergence will be determined by comparing to baseline severity. For events occurring on the day of first taking study medication, it will be assumed to be posttreatment.

The planned summaries for adverse events are provided in [Table KGAD.6.10](#) are described more fully in compound level safety standards and in the adverse event-related PhUSE white paper [Analysis and Displays Associated with Adverse Events: Focus on Adverse Events in Phase 2-4 Clinical Trials and Integrated Summary Document (PhUSE 2017)].

Summary tables as described in [Table KGAD.6.10](#) will be presented for the following periods/analysis populations as indicated. Summary tables will include the number and percentage of patients reporting an event. For events that are gender-specific (as defined by MedDRA), the number of participants at risk will include only patients from the given gender.

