### 6.1.2. General Considerations for Analyses

Treatment period starts after the first injection of study treatment at Baseline Visit (Day 1) and ends after patient completed Week 16 visit or the early termination visit (ETV) (between Day 1 and Week 16). For patients who are randomized but not dosed, the Double-Blinded Treatment Period starts on the date of randomization.

Baseline will be defined as the last available value before the first injection for efficacy and health outcome analyses. In most cases, this will be the measure recorded at Baseline Visit (Day 1). If the patient does not take any injection, the last available value on or prior to randomization date will be used. Change from baseline will be calculated as the visit value of interest minus the baseline value.

For Pruritus Numeric Rating Scale (NRS) and Sleep-Loss due to Pruritus collected via eDiary, the baseline period is the 7-day window prior to the first injection. A patient must have responses on at least 4 of 7 days to calculate a baseline weekly mean. If a patient has responses for 3 or fewer days, the baseline mean value will be considered missing. eDiary data for Pruritus NRS and Sleep-loss due to Pruritus are mapped to study visit per [Appendix 1](#).

For the safety analyses, the following baselines will be used. For safety analyses using a baseline period, the baseline period is defined as the time from Screening Visit to the date/time of the first injection in Treatment Period.

- Treatment-emergent adverse events (TEAEs): baseline will be all results recorded during the baseline period.
- Treatment-emergent abnormal laboratory and vital signs results: baseline will be all results recorded during the baseline period.
- Change from baseline to last observation or to each scheduled post baseline visit for laboratory and vital signs results: baseline will be the last scheduled non-missing assessment recorded during the baseline period.

The randomization to treatment groups is stratified by geographical region (US versus EU versus rest of world), age group (adolescent patients 12 to <18 years versus adults  $\geq 18$  years) and baseline disease severity (IGA 3 versus 4) as described in Section 5.3. The countries will be categorized into geographic regions for analysis (Section 6.3). Unless otherwise specified, the statistical analysis models for Treatment Period will adjust for geographic region, age group and baseline disease severity.

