### 6.14. Safety Analyses

The planned analyses of safety data will be performed with an intent to maintain consistency with compound level standard safety analyses (PSAP). These standards are based on internal standards which were informed by Clinical Data Interchange Standards Consortium (CDISC) standards, regulatory guidance (for example, FDA Clinical Review Template), and cross-industry standardization efforts (for example, Pharmaceutical Users Software Exchange [PhUSE] white papers from the Standard Analyses and Code Sharing Working Group provided in the PhUSE Computational Science Deliverables Catalog).

Safety evaluations will be based on the Modified Safety Population (Treatment Period). A sensitivity analysis will also be conducted on the Safety Population (Treatment Period).

Analysis populations are fully defined in [Table KGAD.6.1](#) while [Table KGAD.6.2](#) describes the treatment groups and the comparisons for each analysis population.

For document writing purposes for safety, tests with two-sided p-values less than 0.05 will be referred to as having strong statistical evidence for a treatment difference, unless otherwise noted. However, p-values should not be over-interpreted for these safety analyses. Except for pre-specified hypotheses, they correspond to data-driven hypotheses and hence are only useful as a flagging mechanism.

Not all displays described in this section will necessarily be included in the CSRs. Any display described and not provided in the CSR would be available upon request. Not all displays will necessarily be created as a “static” display. Some may be incorporated into interactive display tools instead of or in addition to a static display. Any display created interactively will be included in the CSR if deemed relevant to the discussion.

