**Table KGAD.6.10. Summary Tables/Listings Related to Adverse Events**

Analysis	Population (Section 6.1.1)
Overview of AEs	Modified Safety; Safety (sensitivity analysis)
Summary of TEAE by PTs	Modified Safety; Safety (sensitivity analysis)
Summary of TEAE by PTs occurring in $\geq 1\%$ of patients	Modified Safety; Safety (sensitivity analysis)
Summary of TEAE possibly related to study drug by PTs within SOC	Modified Safety; Safety (sensitivity analysis)
Summary of TEAE by PTs within SOC	Modified Safety; Safety (sensitivity analysis)
Summary of TEAE PTs by maximum severity	Modified Safety; Safety (sensitivity analysis)
Summary of SAE by PT within SOC	Modified Safety; Safety (sensitivity analysis)
Summary of AEs leading to treatment discontinuation by PT with SOC	Modified Safety; Safety (sensitivity analysis)
Listing of SAEs (including Death)	ITT
Listing of primary AEs leading to study treatment discontinuation	ITT
Listing of TEAE (for Japan submission only)	Safety

Abbreviations: AE = adverse event; ITT = Intent-to-Treat;

PT = Preferred Term; SAE = serious adverse event; SOC = System Organ Class; TEAE = treatment-emergent adverse event.

Statistical comparisons will be performed using Fisher's exact test. Odds ratio will be provided.

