#### **6.14.2.2. Deaths, Other Serious Adverse Events and Other Notable Adverse Events**

The number and percentage of patients reported with an SAE during the treatment period will be summarized by treatment using MedDRA PT. A listing of SAEs will be provided.

The number and percentage of patients who permanently discontinued from study treatment due to an AE (including AEs that led to death) during the treatment period will be summarized by treatment using MedDRA PT. Events will be ordered by decreasing frequency in the all treatment groups.

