#### **6.14.5. Immunogenicity**

An individual sample is potentially examined multiple times in a hierarchical procedure to produce a sample anti-drug antibody (ADA) assay result and may yield a sample neutralizing ADA (NAb) assay result. Treatment-emergent ADA (TE-ADA) are defined as those with a titer

2-fold (1 dilution) greater than the minimum required dilution if no ADAs were detected at baseline (treatment-induced ADA) or those with a 4-fold (2 dilutions) increase in titer compared to baseline if ADAs were detected at baseline (treatment-boosted ADA). A patient is considered TE-ADA positive when at least 1 postbaseline ADA sample meets the definition of TE-ADA.

Compound level safety standards (described in PSAP) will be followed in the analyses of immunogenicity. Listings of immunogenicity assessments will be provided-along with the summary of specified TEAEs by TE-ADA status for the Safety Population. The summary of TE-ADA and NAb status will be produced for the Modified Safety Population, where the postbaseline period for reporting is the same as described for AEs in Section 6.14.2. Additional assessments of the relationship between immunogenicity and efficacy will be performed as part of the integrated analysis including other Phase 3 lebrizumab AD trials.

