#### **6.14.6. Special Safety Topics including Adverse Events of Special Interest**

This section includes areas of interest whether due to observed safety findings, potential findings based on drug class, or safety topics anticipated to be requested by a regulatory agency for any reason. In general, potential adverse events of special interest (AESI) relevant to these special safety topics will be identified by one or more Standardized MedDRA Query(ies) (SMQs), by a Lilly-defined MedDRA PT listing based upon the review of the most current version of MedDRA, or by treatment-emergent relevant laboratory changes, as described below. Additional special safety topics may be added as warranted.

Unless otherwise specified, the special safety topics will be summarized for the Modified Safety Population and the Safety Population during the Treatment Period as described in Section 6.14.

Full details of the search terms and rules for deriving special safety topics in each of the sections below are described in the compound level safety standards along with information about the types of summaries and listings to be provided. In the event that the listing of terms or analysis changes for a special safety topic, it will be documented in the compound level safety standards which will supersede this document; it will not warrant an amendment to the individual study SAP.

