**Table KGAD.6.14. Summary Tables Related to Eosinophil and Eosinophil-Related AE**

Analysis	Population

Shift table summarizing the number and percentage of participants within each maximum baseline category versus each maximum postbaseline category by treatment
	
Modified Safety; Safety (sensitivity analysis)

Summary of eosinophil-related TEAE by PT
	
Modified Safety; Safety (sensitivity analysis)

Abbreviations: AE = adverse event; PT = Preferred Term; TEAE = treatment-emergent adverse event.

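### SAP safety summaries end at Week 16 or early termination, so the follow-up ADA sample, and any new non-serious AEs recorded then, enter no by-arm summary the SAP names

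*SAP*

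**What the plan says.** SAP 6.1.2 states that the Treatment Period "ends after patient completed Week 16 visit or the early termination visit (ETV"). SAP 5.1.3 describes the safety follow-up visit separately.

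The safety sections then tie their summaries to that period:

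- SAP 6.14: "Safety evaluations will be based on the Modified Safety Population (Treatment Period"). The sensitivity analysis on the Safety Population carries the same restriction.
- SAP 6.14.2, on treatment-emergent AEs (TEAEs): "The treatment period will be included as postbaseline for the analysis".
- SAP 6.14.2.2: "The number and percentage of patients reported with an SAE during the treatment period will be summarized by treatment using MedDRA PT".
- SAP 6.14.6, unless otherwise specified: "the special safety topics will be summarized for the Modified Safety Population and the Safety Population during the Treatment Period".
- SAP 6.14.5, on the summary of treatment-emergent ADA (TE-ADA) and neutralizing-antibody (NAb) status: "where the postbaseline period for reporting is the same as described for AEs in Section 6.14.2".

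The protocol collects data beyond that point. Section 7.11 and Appendix 1 schedule AE review and a PK and ADA draw about 12 weeks after the last injection, for patients who terminate early or do not enter the extension. SAP 6.17 holds the final database lock until follow-up is finished but attaches no analysis to it.

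Protocol 9.10 defines TEAEs by onset on or after the first injection, with no end date, and has them summarized by treatment group. Protocol 9.7 plans descriptive statistics for ADA variables with no period limit.

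**The concern.** The follow-up visit gathers safety and immunogenicity information after dosing has stopped. If every by-arm summary closes earlier, a reader of the planned tables cannot compare arms on new non-serious events from that interval, or see how many patients first met the TE-ADA definition there.

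The gap can be longest for patients who stop early. Under Protocol 8.6.2, patients who discontinue study drug permanently, other than for systemic rescue, go to an early termination visit. Under 8.6.1, patients who leave the study have that visit as soon as possible. Their window can therefore close soon after the last dose, including when an AE was the reason for stopping.

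**Working it through.** **1. The plan's own timing.** The last injection is at Week 14 (SAP 6.9) and follow-up comes 12 weeks later: 14 + 12 = Week 26. This matches the heading of Protocol 7.11.

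**2. Week 16 completer who does not roll over.** The window ends at day 16 × 7 = 112 and follow-up is at day 26 × 7 = 182. The share outside is (182 − 112)/182 = 70/182 = 38%, or 10 of 26 weeks. With the ±3-day windows at both visits:
- late Week 16, early follow-up: (179 − 115)/179 = 64/179 = 36%
- early Week 16, late follow-up: (185 − 109)/185 = 76/185 = 41%

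**3. Early terminator.** Let the last dose be at Week d and the termination visit g weeks later. The documents fix no gap, so g = 0 to 2 is an assumption, and d = 2 and d = 8 are examples. The share outside is (12 − g)/(d + 12):
- d = 2: 10/14 to 12/14 = 71% to 86%
- d = 8: 10/20 to 12/20 = 50% to 60%

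**4. Per 10 non-rollover completers.** Outside the window: 10 × 70/365.25 = 1.9 patient-years. Inside: 10 × 112/365.25 = 3.1 patient-years. Scheduled post-baseline ADA samples are at Week 4, Week 16 (or early termination) and follow-up, so one of three is outside. That gives up to 10 follow-up samples, about 10 × 2/3 ≈ 7 from lebrikizumab if non-rollover is equal by arm at 2:1.

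**5. Where else follow-up data could appear in the SAP.**
- *Serious AEs:* the registry summary (6.19) counts these whether or not they are treatment-emergent, and the SAE listing in Table KGAD.6.10 states no period.
- *ADA results:* the immunogenicity listing (6.14.5) states no period limit.
- *Conjunctivitis and specified infections:* the listings in Tables KGAD.6.16 and KGAD.6.15 state no period limit.
- *Other non-serious AEs:* the registry category for these requires a TEAE, and the only general AE listing is "Listing of TEAE (for Japan submission only"). Both probably carry the 6.14.2 window, if that window governs what counts as a TEAE.
- *Eosinophil-related events and AD exacerbation:* Table KGAD.6.14 has "Summary of eosinophil-related TEAE by PT" and a shift table, and Table KGAD.6.20 has a TEAE summary. Neither includes a listing.
- *Wider-period display:* the ALT versus bilirubin plot (Table KGAD.6.13) covers all periods, but it shows neither AEs nor ADA, and Appendix 1 schedules no chemistry at follow-up.

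No by-arm summary named in the SAP therefore takes in the follow-up ADA sample. On the TEAE reading above, none takes in a new non-serious AE.

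**The case against.** The strongest reply is that the SAP delegates this content. Sections 6.14, 6.14.2, 6.14.5 and 6.14.6 all refer to compound-level safety standards for fuller detail, and for special topics those standards can supersede the SAP. Absence from the SAP does not show that no display is planned. This stands, and it confines the point to what the SAP itself names.

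Second, the SAP's choice is coherent. Exposure, AEs and TE-ADA share one window in which both arms follow the same schedule. After Week 16 only a self-selected group is followed, since every completer may be offered the extension. This justifies keeping the Treatment Period tables as the main displays. It does not argue against a separate descriptive one.

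Third, Protocol 7.11 can be read as recording only AEs already ongoing at termination, which would leave few or no new ones to tabulate. Protocol 8.4.4 and 8.4.4.1, and the AE row of Appendix 1, support recording new ones. The AE half remains conditional on that reading; the ADA half does not.

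A reader might infer more than the documents support:

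- *Follow-up safety data are discarded.* They are not. SAEs can reach the registry summary and the SAE listing, and ADA results stay in the immunogenicity listing. Protocol 9.7 also has ADA influence on concentration profiles evaluated, and further PK/PD work sits in a separate plan.
- *The registry and Japan listing exclude these AEs by rule.* That is an inference. The TEAE definition in SAP 6.14.2 has no end date in its own sentence, the window sentence does not say only, and neither display repeats the limit.
- *The SAP breaks a table promised in the protocol.* Protocol 9.10 also refers to a treatment-period denominator, so the SAP is narrower than the definition without contradicting a specified table.

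**Conclusion.** The point holds in limited form. The SAP's stated window leaves the follow-up ADA sample, and any new non-serious AEs recorded then, out of every by-arm summary it names. It is narrower than Protocol 9.10 and 9.7 and gives no reason.

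The percentages above are shares of one patient's time, not a measure of impact. The documents do not say how many patients terminate early or decline the extension, so no event or ADA count can be derived. The conclusion assumes that new AEs are recorded at follow-up and that the compound-level standards do not already fill the gap. No efficacy result, test or main safety comparison changes. The priority is minor.

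**What to change.** Keep all Treatment Period tables as the main displays, including the TE-ADA/NAb summary. At final lock, add the following, or cite where the compound-level standards already provide them:

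- a descriptive by-arm summary of AEs and AEs of special interest with onset after Week 16 or the early termination visit, with number and time at risk and no tests;
- a by-arm count of patients with a follow-up ADA sample and of those first TE-ADA positive at follow-up.

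Reconcile the TEAE period in SAP 6.14.2 with Protocol 9.10, and state in Protocol 7.11 whether new as well as ongoing AEs are recorded.

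The cost is about one sentence each in SAP 6.14.2, SAP 6.14.5 and Protocol 7.11, plus two tables. The drawback is that the follow-up subset is self-selected and of unknown size. Non-rollover completers also have three scheduled post-baseline ADA samples against two for rollover patients, so merging follow-up into one TE-ADA status would give them an extra chance of a positive result. The new displays must stay separate from the Treatment Period summaries and out of the Fisher-tested percentages.

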**Table KGAD.6.10. Summary Tables/Listings Related to Adverse Events**

Analysis	Population (Section 6.1.1)
Overview of AEs	Modified Safety; Safety (sensitivity analysis)
Summary of TEAE by PTs	Modified Safety; Safety (sensitivity analysis)
Summary of TEAE by PTs occurring in $\geq 1\%$ of patients	Modified Safety; Safety (sensitivity analysis)
Summary of TEAE possibly related to study drug by PTs within SOC	Modified Safety; Safety (sensitivity analysis)
Summary of TEAE by PTs within SOC	Modified Safety; Safety (sensitivity analysis)
Summary of TEAE PTs by maximum severity	Modified Safety; Safety (sensitivity analysis)
Summary of SAE by PT within SOC	Modified Safety; Safety (sensitivity analysis)
Summary of AEs leading to treatment discontinuation by PT with SOC	Modified Safety; Safety (sensitivity analysis)
Listing of SAEs (including Death)	ITT
Listing of primary AEs leading to study treatment discontinuation	ITT
Listing of TEAE (for Japan submission only)	Safety

Abbreviations: AE = adverse event; ITT = Intent-to-Treat;

PT = Preferred Term; SAE = serious adverse event; SOC = System Organ Class; TEAE = treatment-emergent adverse event.

Statistical comparisons will be performed using Fisher's exact test. Odds ratio will be provided.

#### **6.14.2.1. Common Adverse Events**

The number and percentages of patients with TEAEs will be summarized by treatment using MedDRA PT for the common TEAEs (occurred in  $\geq 1\%$  before rounding in any column in the table).

#### **6.14.2.2. Deaths, Other Serious Adverse Events and Other Notable Adverse Events**

The number and percentage of patients reported with an SAE during the treatment period will be summarized by treatment using MedDRA PT. A listing of SAEs will be provided.

The number and percentage of patients who permanently discontinued from study treatment due to an AE (including AEs that led to death) during the treatment period will be summarized by treatment using MedDRA PT. Events will be ordered by decreasing frequency in the all treatment groups.

### **6.14.3. Clinical Laboratory Evaluation**

As described more fully in compound level safety standards and in the laboratory-related PhUSE white papers (PhUSE 2013; PhUSE 2015), the clinical laboratory evaluations will be summarized as described in [Table KGAD.6.11](#).

**Table KGAD.6.11. Analysis for Clinical Laboratory Evaluations**

Analysis	Population
Box plots of observed values by visit Box plots for change values by visit	Modified Safety; Safety (sensitivity analysis)
Change from baseline to last observations. ANCOVA model with treatment and baseline value in the model.	Modified Safety; Safety (sensitivity analysis)
Scatter plots of baseline-by-maximum values and baseline-by-minimum values	Modified Safety; Safety (sensitivity analysis)
Treatment-emergent abnormal high lab values (that is, patients shifting from a normal/low maximum baseline value to a high maximum postbaseline value) or abnormal low lab values (that is, patients shifting from normal/high minimum baseline value to a low minimum postbaseline value)	Modified Safety; Safety (sensitivity analysis)
Shift tables showing the number of patients who shift from each category of maximum (minimum) baseline observation to each category of maximum (minimum) postbaseline observation. Here categories may be low, normal, or high with cut-offs defined in the compound level safety standards.	Modified Safety; Safety (sensitivity analysis)
Listing of abnormal findings for laboratory analyte measurements, including qualitative measures	All Enrolled

Abbreviation: ANCOVA = analysis of covariance.

